9.1 Adverse Events (AE)

“Adverse Event” (AE) is any adverse medical event that occurs after administration of investigational drug and may manifest itself as a symptom, sign, disease or abnormal laboratory test, but is not necessarily causally related to the investigational drug.

AEs in this trial are collected from the time of the first dose of study drug to the completion of the last visit or trial process planned in the protocol. However, for the protection of subjects' rights, the recording of adverse events in this study starts with the signing of Informed Consent Form. The incidence of adverse events in this trial is calculated based on adverse events that occur after the first dose. However, the following conditions should not be recorded as AEs:

- Pre-existing conditions identified at screening (for example, laboratory tests, vital signs, etc. show clinically significant abnormalities at screening that, in the judgment of the investigator, exist prior to the subject's informed consent); such conditions should be recorded as medical history/concomitant disease.
- Medical and surgical examination process (such as liver biopsy, endoscopy); however, the diseases that cause these tests may be adverse events.
- Existing concomitant diseases or pre-existing signs and symptoms at screening have progressed as expected, but have not worsened.

The sources of adverse events include:

- Subject's responses to questions about his/her health status (non-leading questions at each visit such as “How are you feeling since your last visit”).
- Symptoms spontaneously reported by the subject.
- Changes or abnormal findings or examinations that are assessed by the investigator to be clinically significant.
- Other information related to the health of the subject that is made known to the investigator (e.g. hospitalization).

9.2 Serious Adverse Events (SAE)

Each AE is to be classified by the Investigator as SERIOUS or NON-SERIOUS.

An SAE is generally an adverse event that results in any one or more of the following outcomes, including:

- Leading to death.
- Life-threatening (It refers to the immediate risk of death, not the death that may occur in the future when the disease progresses).
- Leading to hospitalization or prolonged hospitalization; this does not include elective surgery or prolonged hospitalization or prolonged hospitalization due to non-adverse events.

- Leading to permanent or significant loss of function.
- Congenital anomaly/birth defects
- Other medically important events: They may not be immediately life-threatening, lead to death or hospitalization, but are also usually considered serious if medical measures are required to prevent one of the above. Examples include important treatment in the emergency room or allergic bronchospasm at home, cachexia or convulsions requiring no hospitalization, development of drug dependence or addiction.

9.3 Suspected Unexpected Serious Adverse Reaction

A Suspected Unexpected Serious Adverse Reaction (SUSAR) refers to a serious adverse reaction whose nature or severity is beyond the information available in the investigator's brochure of the test drug, the package insert of the marketed drug or the summary of product characteristics.

The sponsor will promptly report SUSARs to all investigators and clinical study sites participating in the clinical trial; the sponsor will report any known SUSARs to the drug regulatory agency and the health administrative department as required.

9.4 Assessment of Adverse Event Correlation

The correlation between the adverse event and the study drug is assessed by the investigator according to the following:

☆ Definitely related to the study drug

There is evidence of taking the study drug; the occurrence of adverse events and the time sequence of taking the study drug are reliable; the occurrence of adverse events is explained more reasonably by the study drug than by other reasons; the withdrawal reaction is positive; the repeated drug use test is positive; the pattern of adverse events is consistent with previous understanding of this drug or this type of drug.

☆ Probably related to the study drug

There is evidence of taking the study drug; the occurrence of adverse events and the time sequence of taking the study drug are reliable; the occurrence of adverse events is explained more reasonably by the study drug than by other reasons; the withdrawal reaction is positive.

☆ Possibly related to the study drug

There is evidence of taking the study drug; the occurrence of adverse events and the time sequence of taking the study drug are reliable; adverse events may be caused by the study drug or by other reasons; the withdrawal reaction is positive.

☆ Possibly unrelated to the study drug

There is evidence of taking the study drug; adverse events are more likely to be caused by other reasons; the withdrawal reaction is negative or ambiguous; the repeated drug use test is negative or ambiguous.

☆ Definitely unrelated to the study drug

The subject does not take the study drug; or the occurrence of adverse events and the time sequence of taking the study drug are not reliable; or there are other significant reasons that lead to adverse events.

9.5 Severity of Adverse Events

The investigators will categorize the severity of each adverse event by describing the clinical symptoms with reference to the five-grade judgment criteria developed by NCI CTCAE V5.0. The severity classification is as follows.

- Grade 1: mild, asymptomatic or slight; only seen in clinical practice or diagnosis; no treatment is required;
- Grade 2: minor, local, or non-invasive treatment is required; age-appropriate instrumental activities of daily living are limited*;
- Grade 3: Serious or medically significant but not immediately life-threatening; leading to hospitalization or prolonged hospitalization; disabling; self care activities of daily living are limited**;
- Grade 4: life-threatening, requiring emergency treatment;
- Grade 5: AE-related deaths.

*Instrumental activities of daily living refer to cooking, shopping for clothes, telephone use, money management, etc.

**Self care activities of daily living refer to bathing, dressing and undressing, eating, washing hands and face, taking medication, etc., in a non-bedridden state.

9.6 Recording of Adverse Event

Any adverse event, whether serious or not, and whether or not related to the study drug, must be recorded on the case report form. Patients who withdraw due to any adverse event should be followed up by the investigator until recovery or stabilization, or until baseline levels are reached, or until clinical manifestations is judged by the investigator to be basically stable that require no further follow-up, and should be recorded in the original document. Follow up can be divided into hospitalization, outpatient, home visit, telephone, communication and other forms according to the severity of adverse events.

9.7 Name of Adverse Event

The name of an adverse event should be a medical term and a medical diagnosis should be used in preference. That is, if multiple symptoms, signs and abnormal laboratory values can be described or attributed to the manifestation of a disease or impairment, this is treated as an adverse event. If a definitive diagnosis cannot be made, symptoms/signs should be used. When the later diagnosis is clear, the record is updated to replace the previous signs/symptoms with the diagnosis.

9.8 Start and End Time of the Adverse Event

The onset time of the AE is the time when the subject first experiences the AE or related symptoms and signs, not the time reported by the subject or the time when the investigator is informed. If the AE is a clinically significant abnormal laboratory test or auxiliary examination, the onset time is recorded as the sampling or examination time.

The end time of the AE is the date when the AE or AE-related symptoms and signs cease. If the AE is a clinically significant abnormal laboratory test or auxiliary examination, the end time is the sampling or examination time.

If the same AE occurred two or more times in the same subject and the subject recovered between the two events, it is counted as two AEs.

The severity of the AE increased without adding an additional AE record.

The SAE report needs to provide:

- 1) Time of event occurrence (first symptom or laboratory test abnormality);
- 2) Time when the event reaches the SAE severity standard;
- 3) Time when the event ends.

9.9 Outcome of adverse events

The researchers followed up the subjects' adverse events and filled in the adverse event outcomes/results, including recovery, recovery with sequelae, improved, not improved, died, and unknown.

9.10 Reporting Process of Serious Adverse Events

Serious adverse events occurring during the clinical trial, whether or not related to the study drug, must be reported immediately to the sponsor by the investigator, who must complete an adverse event attached table and notify the sponsor and the contract research organization within 24 hours. The investigator should then provide a detailed, written follow-up report in a timely manner, which should adhere to the 24-hour time limit and the reporting process described above. The investigator should also report to the research institution, ethics committee, etc. of this site as required by the study site.

In the event that the sponsor and the investigator cannot agree on the causal relationship between the adverse event and the drug, expedited reporting should also be conducted if either party determines that a correlation with the trial drug cannot be excluded. Therefore, the sponsor requires to provide supporting documents of serious adverse events (such as attached table of adverse events, checklist), and the study site should assist in submitting information to the sponsor as soon as possible.

For the reporting of death events, the investigator should provide the sponsor and the Ethics Committee with required data, such as autopsy report and final medical report. For fatal or life-threatening SAE events, the investigator should report the follow-up report and complete the follow-up information within 7 days of the initial report whenever possible.

The investigator is the first responsible person for the collection and follow-up of adverse events/serious adverse events and should follow up until the event is over, the condition is stable, a reasonable explanation has been given, loss to follow-up or death; the investigator should timely provide follow-up information as requested by the sponsor, and ensure the accuracy and consistency of the report content.

The investigator should sign for and read the safety information of the clinical trial provided by the sponsor in a timely manner, and consider whether the subject's treatment should be adjusted accordingly. If necessary, the investigator should communicate with the subject as early as possible and report SUSARs provided by the sponsor to the Ethics Committee.

9.11 Pregnancy

The investigator should inform the subjects that any pregnancy that occurs during the study and within 6 months after the completion of the study must be reported to the investigator. Pregnancy is not an adverse event, but if the investigator learns that the subject or her spouse is pregnant, it must be reported to the principal investigator, ethics committee, contract research organization and sponsor of the center within 24 hours.

Researchers should advise subjects and discuss the risks of continuing pregnancy and possible effects on the fetus. Female subjects should be advised to stop taking the drug. Subjects should continue to be followed up until 1 month after termination of pregnancy or delivery.

Pregnancy in the partner of a male subject during the study should also be reported to the investigator and sponsor. Partners of patients should also be advised and followed as described above.

10. Data Management and Statistical Analysis

An independent third party will be responsible for data management and biostatistics, participate in trial design and program implementation, be responsible for clinical data management and statistical analysis, and complete data management reports and statistical analysis reports.

10.1 Randomization

Approximately 120 patients will be randomized in a 1:1 ratio to either IVIEW-1201 or positive control drug. This trial adopts a randomized block method to randomly assign subjects, using a central randomization system. The Interactive Web Response System (IWRS) will be used for the allocation of randomization numbers and the drugs will be dispensed according to the drug numbers assigned by the IWRS. The drug number will be recorded in the subject's eCRF. There is competition for enrollment among the study sites participating in this study. The investigators at each study site should log into the system after screening all eligible subjects and fill in the screening information, so that the subjects can be randomized and obtain a randomization number.

The authorized investigator will obtain a randomization number of each randomly assigned patient through the randomization system, prompting the results of the random treatment allocation. And obtain the corresponding drug number.

10.2 Data Management

10.2.1 Original Data and Original Documents

Original data

Original data is all the information in the original records generated by clinical findings, observations or other activities in the trial and their qualified copies, which are necessary for the restoration and evaluation of the trial. Original data is included in the original record.

Original record

Original records are the earliest documents, data and records (e.g. hospital records, clinical and office charts, laboratory records, memoranda, subject diaries or evaluation forms, drug dispensing records, data recorded by automated instruments, qualified copies or duplicates that have been verified as accurate copies, microfilm, photographic negatives, microfilm or magnetic media, x-rays, subject files and records kept by pharmacies, laboratories and pharmaceutical technical departments participating in clinical trials).

Clinical trial specific original data

The investigator must keep the records of the subjects.

The subject's medical history results and other clinically relevant outcomes, demographic data and AEs should be recorded in specific original records and then transcribed into the Case Report Form (CRF) for each subject. Laboratory results will be transcribed into the CRF by the investigator and labeled as normal,

abnormal not clinically significant or abnormal clinically significant. If necessary, specific exceptions will be described in detail in the CRF.

CRF

This trial uses an electronic case report form, the content of which is collected by the researcher or his/her authorized personnel through the clinical electronic data collection and management system.

- 1) All subjects who have signed the informed consent form must fill in the case report form in accordance with the instructions, and record any items in the case report form carefully and in detail;
- 2) All data in the case report form must be checked with the subject's original document data to ensure accuracy;
- 3) Data that are significantly higher or outside the clinically accepted range must be verified and, if necessary, judged by the researcher;
- 4) For other details, please refer to the electronic case report form filling guide.

After the completed electronic case report form is reviewed by the clinical monitor, the data manager will conduct data verification and management. After data collection and cleaning are completed, the researcher will sign and confirm online.

The original subject file is the original record of the subject kept by the trial unit. The trial data must be entered into the CRF in a timely manner.

The completed CRF is the exclusive property of the sponsor and cannot be provided to a third party in any form without the sponsor's written permission, except for the authorized representative of the relevant regulatory agency or ethics committee (EC).

10.2.2 Data management process

- 1) This study adopts an electronic data management system. Construction of electronic CRF: The data administrator constructs the electronic CRF (eCRF) according to the study protocol.
- 2) Permission allocation: The data administrator creates separate accounts and grants different permissions according to the different identities (e.g. data entry staff, investigator, CRO). The data entry person has the permission to enter, modify, question and feedback data; the principal investigator has the permission to modify, browse, question feedback and sign electronically; the CRO has the permission to browse and send queries; the data administrator has the permission to browse, send queries and lock data.
- 3) Data entry: The clinical investigator or a data entry person (clinical coordinator) appointed by the investigator enters data from the study medical record into the eCRF in a timely and accurate manner. For external data, the appropriate protocols for external data transfer need to be developed during the operation of the project. At least 2 transfers should be made before the database is locked in order to confirm the accuracy of external data. After the database is locked, the data is needed to be transferred to the statistical analysis unit according to the external data transfer protocol.
- 4) Sending and resolution of queries: The CRO, the data administrator, the CRO send all queries through the EDC system, and the data entry person or the investigator answers the questions and correct incorrect data. Queries can be sent repeatedly if necessary and all records are kept in the eCRF.

5) Modification and review of data: Data can be modified by the data entry person or the investigator after verifying the data, and the reasons for the modifications need to be filled in on the eCRF. The investigator has the permission to sign all final data electronically.

6) Data locking and export: After all data has been verified for accuracy, the data administrator locks the data. Any modifications required after the data has been locked need to be signed off by the sponsor, investigator, data entry person, CRO and data administrator before implementation. All data is eventually exported by the data administrator and handed over to the statistician for analysis.

10.3 Statistical Analysis

10.3.1 Selection of statistical analysis data set

- 1) Full Analysis Set (FAS): All subjects randomized and for whom the data of at least one post-dose efficacy indicator is collected. Only the following randomized subjects are excluded: Subjects who violates key eligibility criteria, who are not treated with the investigational drug, and who have no observed data after randomization.
- 2) Per Protocol Set (PPS): A subset of the FAS, excluding subjects with significant protocol violations that may affect the primary efficacy evaluation based on the FAS.
- 3) Safety Set (SS): All subjects who have used the study drug at least once.

The efficacy analysis is mainly based on the FAS, but also on the PPS; the SS is used for safety analysis.

10.3.2 Statistical analysis method

This study will use SAS software version 9.4 or above for statistical analysis.

The statistical description of quantitative indicators will calculate the number of subjects, mean, standard deviation, median, minimum and maximum (25% quantile Q1, 75% quantile Q3 where necessary), the statistical description of categorical indicators will calculate the number of subjects and percentage.

The T-test or non-parametric comparison is used for inter-group comparison of quantitative indicators, and the chi-square test or Fisher's exact probability method is used for inter-group comparison of categorical indicators.

10.3.3 Missing value imputation

For primary efficacy indicators, missing data are imputed using appropriate methods. If applicable, data from the last observation before dropout may be used to impute (LOCF method), and other missing value imputation methods should be explored for sensitivity analysis.

11.1 Subject Withdrawal Criteria

Subjects will be removed from the study for the following reasons:

- 1) Death;
- 2) Allergy or intolerance to the study drug;
- 3) Pregnancy events during the course of the study;
- 4) Self-withdrawal by the subject/guardian;
- 5) Subject is lost to follow-up;
- 6) Adverse events occurring in subjects that, in the judgment of the investigator, will adversely affect the subject during the continued treatment period;
- 7) Serious violation of the protocol by the subject which, in the judgment of the investigator, affects the evaluation of the trial results;
- 8) Other reasons for subject withdrawal in the judgment of the investigator.

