	
Safety analysis
 
Adverse event: Treatment-Emergent Adverse Event (TEAEs) should be focused on, i.e. treatment-emergent adverse events. The χ^2 test or Fisher's exact probability method is used to compare the incidence of adverse events in each group and the incidence of adverse events related to the study drug. All adverse events will be coded using the Medical Dictionary for Regulatory Activities (MedDRA) and the number of cases, incidence and frequency of each type of adverse event occurring during the trial will be summarized by SOC/PT. The adverse events occurring in this trial will be tabulated and described.

--	---

Overview of study flow chart of IVIEW 1201

Visit schedule	Visit 1	Visit 2	Visit 3	Visit 4/ EOT	Visit 5/ EOS
Test stage	Screening/Baseline/Day 1	Day 3	Day 6	Day 8	Day 14/ Early withdrawal
Visit window period				(± 1 days)	(± 1 days)
Signing of Informed Consent Form	X				
Inclusion and exclusion criteria	X				
Randomization	X				
Demographic data ¹	X				
History taking ²	X				
Subjective Symptoms Score ³	X	X	X	X	X
Objective Clinical Score ⁴	X	X	X	X	X
Collection of conjunctival sac secretion ⁵	X	X	X	X	X
Vital signs ⁶	X	X	X	X	X
Pregnancy Test ⁷	X				X
Corneal endothelial cell count	X				X
Best-corrected visual acuity	X	X	X	X	X
Corneal fluorescein staining	X	X	X	X	X
Slit-lamp examination	X	X	X	X	X
Intraocular pressure measurement	X	X	X	X	X
Fundus examination	X				X
12-lead ECG examination	X				
Drug allocation ⁹	X				
Study drug administration ¹⁰	X	X	X		
Drug compliance assessment		X	X	X	
Recoding of concomitant medications	X	X	X	X	X
Adverse events ¹¹	X	X	X	X	X
Check of diary card		X	X	X	
Return of drugs				X	X

1.Demographic information: date of birth, gender, ethnicity, height, weight.

2.Medical history collection: including past medical history, surgical history, current medical history (time of onset, cause, etc.), comorbidities, medication history, etc. Any clinically significant examination results other than the research disease found during the screening period should be recorded as medical history.

3.Symptom scoring: Four symptoms (pain, foreign body sensation, photophobia, and tearing) were scored using a 3-point scale (0 = none, 1 = mild, 2 = moderate, 3 = severe). Under the guidance of the researchers, the subjects scored according to the actual situation on the day before the visit and checked in the record form.

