2.2 Endpoints

2.2.1 Primary Endpoints

Clinical cure rate: The proportion of subjects with a score of 0 (on a 3-point scale) for bulbar conjunctival congestion and 0 (on a 3-point scale) for conjunctival secretion/exudation at Visit 4/End of Treatment (EOT) (Day 8±1 day) and Visit 5/End of Study (EOS) (Day 14±1 day).

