6.3 Visit 4 (D8 ± 1 day) End of Treatment

Subjects will return to the study site for a visit on Day 8±1 during the treatment period and complete the following:

- 1) Vital signs (temperature, heart rate, blood pressure)
- 2) Subjective Symptoms Score
- 3) Objective Clinical Score

- 4) Best-corrected visual acuity
- 5) Corneal fluorescein staining
- 6) Slit-lamp examination
- 7) Intraocular pressure measurement
- 8) Collection of conjunctival sac secretion
- 9) Return of investigational drug, recovery and check of diary card, and evaluation of drug compliance.
- 10) Recording of adverse events
- 11) Recording of concomitant medications

If a subject forgets to return the investigational drugs, they can be returned at Visit 5. The treatment with the investigational drug shall be terminated at the end of this visit. If the investigator determines that continued treatment is still required (IVIEW-1201 needs to be discontinued) based on the subject's symptoms and signs, the specific treatment regimen will be determined by the investigator and recorded in the eCRF. The subject will need to remain in the study until Visit 5/EOS (Day 14±1 day).

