6.4 End of Study period: Visit 5 (D14 ± 1) End of Study

Subjects will complete the following:

- 1) Vital signs (temperature, heart rate, blood pressure)
- 2) Subjective Symptoms Score
- 3) Objective Clinical Score
- 4) Best-corrected visual acuity
- 5) Corneal fluorescein staining
- 6) Slit-lamp examination
- 7) Intraocular pressure measurement
- 8) Fundus examination
- 9) Corneal endothelial cell count
- 10) Serum Pregnancy
- 11) Recording of adverse events
- 12) Recording of concomitant medications

Subjects who have not returned the investigational drugs at Visit 4 should return the investigational drugs. Subjects who withdraw early should complete the last visit in accordance with the various tests, if possible.

See Appendix 1: Symptom Scoring Criteria and Appendix 2: Evaluation criteria of comprehensive efficacy for the specific criteria for scoring the symptoms and signs mentioned above.

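### Section 11.1 does not separate stopping study drug from leaving follow-up, so scheduled Day 8 and Day 14 scoring is not secured for subjects removed for intolerance, adverse events or violations

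*Combined protocol and SAP*

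**What the plan says.** Section 11.1 opens with "Subjects will be removed from the study for the following reasons". The eight reasons include "Allergy or intolerance to the study drug" (item 2), "Adverse events occurring in subjects that, in the judgment of the investigator, will adversely affect the subject during the continued treatment period" (item 6) and "Serious violation of the protocol by the subject which, in the judgment of the investigator, affects the evaluation of the trial results" (item 7). They stand in one list with death, the subject's own withdrawal, loss to follow-up, pregnancy and an open category left to the investigator.

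The primary endpoint (section 2.2.1) is clinical cure, meaning a score of 0 on both bulbar congestion and secretion, assessed at Visit 4 (Day 8±1) and Visit 5 (Day 14±1).

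Four provisions bear on subjects who leave early:

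- Section 6.4: "Subjects who withdraw early should complete the last visit in accordance with the various tests, if possible". The flow chart labels the shared column "Day 14/ Early withdrawal".
- Section 9.6: anyone who withdraws because of an adverse event is followed until that event resolves or stabilises.
- Section 10.3.1: the FAS needs at least one post-dose efficacy value.
- Section 10.3.3: missing primary data are imputed by methods left open, with LOCF as an option and other methods as sensitivity analyses.

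Section 6.3 handles a related case differently. A subject whose study drug ends at Visit 4 and who needs other treatment is kept: "The subject will need to remain in the study until Visit 5/EOS (Day 14±1 day". Footnote 12 of the flow chart says the same.

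**The concern.** Only death, withdrawal of consent and loss to follow-up inherently end data collection. Intolerance and adverse events are reasons to stop a drug, and item 6 is itself worded around continued treatment. Section 11.1 nevertheless gives all of them the same consequence, departure from the study.

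Followed as written, the rule creates missing primary outcomes for reasons tied to treatment. Section 3.5 says that the two products differ in how they feel on application and that subjects cannot be blinded. Removals for intolerance may therefore be unequal between arms, and the comparison of cure rates would then depend partly on how the gaps are filled.

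Item 7 adds a different kind of removal. It uses the effect of a violation on the evaluation of results as a reason to end observation, although section 10.3.1 already handles such violations by excluding the subject from the PPS.

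**Working it through.** The plan gives no figure to reproduce. Section 3.4 says that no sample-size calculation was made, and no cure rate, dropout rate or margin is stated. The check is therefore a comparison of provisions, followed by an illustration of scale.

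**Step 1. What is secured for a removed subject**

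| Provision | What it yields | Does it secure a Day 8 or Day 14 score? |
|---|---|---|
| 6.4 and flow chart | One exit assessment, where feasible, including the objective score | No. Timing is unstated, as is whether it counts as Visit 5 |
| 9.6 | Follow-up of the adverse event | No. Efficacy is not scored |
| 10.3.3 | LOCF or another method | No. A value is assigned, not observed |
| 6.3 and footnote 12 | Retention to Visit 5 | Yes, but only for subjects who reach Visit 4 |

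No other section schedules efficacy scoring for these subjects. Removal before Visit 4 puts both time points at risk; removal after Visit 4 puts only Visit 5 at risk. A subject removed before the first scheduled post-dose score (Day 3) who has no exit visit has no post-dose efficacy value, and so does not meet the FAS definition.

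**Step 2. Likely direction under LOCF**

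Entry requires a score of at least 1 on both signs (section 4.1). Section 1.1 describes the disease as self-limiting, resolving untreated within 10 to 14 days. A score from the first days, carried forward, would therefore tend to record non-cure for someone who might be clear by Day 14. If removals were more frequent in one arm, that arm would tend to look worse.

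**Step 3. Scale**

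Inputs: n = 60 per arm (section 3.1). The number d removed from one arm before Visit 4 and the cure rate p are assumptions. No removals are assumed in the other arm.

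Width between counting all removed as not cured and all as cured = d/60:

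- d = 3: 3/60 = 5 points
- d = 6: 6/60 = 10 points
- d = 9: 9/60 = 15 points
- d = 12: 12/60 = 20 points

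Example with p about 80% and d = 6 in the test arm, so that 43 of the 54 remaining subjects are cured:

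- removed counted as not cured: 43/60 = 71.7%
- remaining subjects only: 43/54 = 79.6%
- removed counted as cured: 49/60 = 81.7%
- control: 48/60 = 80.0%

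The observed difference runs from −8.3 to +1.7 points on the same data.

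For comparison, the 95% half-width for the difference with equal rates is 1.96 × √(2p(1−p)/60):

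- p = 0.6: 1.96 × √(0.48/60) = 17.5 points
- p = 0.7: 1.96 × √(0.42/60) = 16.4 points
- p = 0.8: 1.96 × √(0.32/60) = 14.3 points

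At 10% to 20% removal in one arm, the undetermined part (10 to 20 points) is of the same order as the sampling error. At 5% it is about a third of it (5/17.5 = 0.29; 5/14.3 = 0.35).

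**The case against.** The strongest reply is that the plan does not abandon these subjects. Adverse events are followed to resolution, an exit assessment is requested, and section 10.3.3 provides for imputation with sensitivity analyses. Counting withdrawal for intolerance as not cured is a well-defined rule for a binary cure endpoint and needs no later score. The protocol's own tolerability evidence is also favourable: section 1.2.1 reports no dropouts for eye-drop intolerance in a 459-child trial of 1.25% povidone-iodine. This is an exploratory Phase II study with no confirmatory claim.

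Much of this stands, and it rules out several stronger readings that a reader might infer:

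- *Removed subjects cease to be followed.* Section 9.6 says otherwise for adverse events. What is not secured is timed efficacy scoring.
- *The exit visit takes place at the moment of withdrawal and so cannot supply the endpoint.* Section 6.4 gives no timing, and the flow chart shares the column with Day 14. The defect is that timing and analytic use are unstated.
- *Item 7 is an exclusion from the FAS.* Removal under item 7 is not among the FAS exclusions in section 10.3.1. Such a subject stays in the FAS if any post-dose efficacy value exists, with later values missing. Nor does the plan say that unblinded staff make this judgment.
- *No imputation rule can help.* A non-cure rule is available, but the plan does not adopt it. Any rule rests on assumptions that the data cannot test.

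The paediatric evidence concerns another formulation and population. It suggests that the rate may be low, but does not establish it here. A low rate would also make retention cheaper.

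**Conclusion.** The concern holds in this form: section 11.1 merges stopping drug with leaving the study, and no other section secures Day 8 and Day 14 scoring for subjects removed before Visit 4, or Day 14 scoring for those removed later. This is out of step with section 6.3, which keeps subjects in the study after drug ends at Visit 4.

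The resulting missingness may differ by arm because subjects are unblinded and the products feel different. Whether it will differ, and by how much, cannot be determined from the documents. The 5 to 20 points of indeterminacy rest on assumed removals of 3 to 12 of 60 in one arm. They are outer bounds, reached only if all removed subjects have the same outcome. The 14 to 18 point half-width rests on assumed cure rates of 80% to 60% in both arms.

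This is a worthwhile, inexpensive improvement to an exploratory trial meant to inform Phase III. It is not a flaw that invalidates the trial.

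**What to change.** Reconcile section 11.1 with sections 6.3 and 6.4:

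1. Divide 11.1 into reasons for discontinuing study drug and reasons for leaving follow-up, the latter being death, withdrawal of consent and loss to follow-up.
2. Keep the scheduled Visit 4 and Visit 5 outcome and safety assessments for consenting subjects who stop drug. Say how this applies to pregnancy (item 3, to be aligned with the continued follow-up in section 9.11) and to the open category (item 8).
3. Make protocol violation a reason for PPS exclusion under section 10.3.1, and not for ending data collection.
4. State in sections 6.4 and 10.3.3 when exit scores are taken, whether they count as Visit 4 or Visit 5 data, and how they enter the primary analysis.

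The cost is protocol wording and a few already-scheduled visits for subjects off drug, with at most 14±1 days of follow-up. Some will decline to attend, so the gap would shrink without necessarily closing. The change leaves untouched when and why drug is stopped.
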